Microbiota composition analysis. As indicated above, stool samples before and after TUDCA treatment will be collected for potential future analysis of microbiota. In the event that we proceed with metagenomic profiling (which would be based on the objective responses noted) microbial community composition will be determined by 16s metagenomic sequencing using the Illumina MiSeq platform. Libraries will be prepared in-house according to Illumina protocols and pooled libraries will be sent to the SBPMDI for deep sequencing. The resulting sequence data will be analyzed with the current version of Qiime ³⁹.

We recognize that TUDCA treatment may not have a significant impact on gut microbiota composition, as our preliminary data from IBD mouse models showed and for this reason will collect stool samples but not undertake metagenomic profiling at this time.

Future analyses. We will biobank tissues, stool and serum for deeper immunologic analyses that may be pursued with additional funding from alternative sources. This study will provide a rich resource for expanded immunological studies and will bank biospecimens (snap frozen, RNA later tissue, serum, stool) for future studies including full cytokine profiles and innate/adaptive immune readouts. These will be processed and stored in our NIDDK sponsored Digestive Diseases Research Center Biobank Core. Stool will also be stored for future microbial/metabolome analyses.

6 Statistical Plan and Outcome Analyses

ER stress and cell death markers. We expect that TUDCA treatment will reduce ER stress in colon biopsy tissues from subjects with symptomatic ulcerative colitis (UC), as judged by expression levels of ER stress markers as we have observed in IBD mouse models. Colon biopsy samples from inflamed and (if available) adjacent non-inflamed colon before and after 6 weeks of TUDCA treatment will be harvested for analysis listed below.

As the primary study endpoint, we will assess the change in ER stress markers, including eIF2 α phosphorylation, XBP1s and BIP/GRP78, in colon biopsy tissues before and after 6 weeks of TUDCA treatment.

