BIP, XBP1 splicing, phosphorylated eIF2 α will be assessed by Western blot and RT-PCR and immunohistochemistry (IHC). Other ER stress markers, such as PERK, ATF4, CHOP, IRE1 α and ATF6 α will also be examined. In addition, we expect that cell death markers in colon biopsy tissues will also be downregulated, including cJUN, JNK, cleaved caspase 2 and cleaved caspase 3. We will also monitor expression of inflammatory cytokines, IL-1B, TNF α , IL-6 and IFN γ . Additional samples aliquots will be saved (flash frozen and RNAlater) for future studies evaluating adaptive and innate immune readouts.

[name], the co-PI of this study, has a broad background in ER stress and cell death, and discovered the therapeutic role of TUDCA in IBD mouse models with support from CCFA. His laboratory has extensive experience in evaluation of ER stress, inflammation and cell death markers by western-blotting, PCR and IHC in both mouse models and human samples. All the colon biopsy samples will be sent under dry ice for analysis by [name] laboratory. [name], a Research Associate in [name] laboratory will be responsible for analyzing and processing data from the clinical samples.

Significance of primary outcomes: Changes in ER stress markers will clarify the mechanisms through which TUDCA may act to alleviate inflammation in colon tissue of subjects with UC.

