We anticipate that TUDCA therapy will reduce ER stress and promote mucosal healing. As TUDCA has the potential to increase stool frequency, it is important to measure efficacy through objective measures (endoscopy and histology) as well as clinical symptoms. Thus, we will obtain a complete Mayo UC score at weeks 0 and 6 and a partial (no endoscopic subscore) at weeks 2 and 4.32 Biopsies will be obtained at both

endoscopic procedures and objectively scored by the Goebes index. Thus, secondary endpoints will include the following using FDA recommended UC Clinical trial guidelines⁴¹:

- 1) Mucosal Healing: A decrease of at least 1 point on the Mayo endoscopic subscore with a final score of 0 or 1 will be used as a marker of mucosal healing.
- 2) Clinical Response: A decrease in Mayo Score of ≥ 3 points and a decrease in Mayo Score of ≥ 30% from baseline and a decrease in the rectal bleeding score of ≥ 1 or an absolute rectal bleeding score of 0-1.
 - a. Clinical Remission will also be recorded if achieved as defined by a total Mayo Score of ≤2 with no subscore >1 and improvement of endoscopic appearance of the mucosa (Mayo 0 or 1).
- **3) Histologic activity:** *Histologic disease activity.* Colon biopsy samples will be harvested and fixed as described. H&E stained sections will be evaluated for tissue damage and inflammation by a gastrointestinal pathologist in a double-blinded manner, using the simplified Geboes histology index^{34, 35}

We expect that TUDCA treatment will significantly alleviate inflammation in colon tissues, which will be correlated with increased plasma concentration of TUDCA or the deconjugated form UDCA. We will collect stool samples both before and after TUDCA treatment for potential (longer range) studies of gut microbiota composition.

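### No masking to visit and no same-run pairing is specified for the primary ER-stress assays, although the secondary histology is read blinded

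*Combined protocol and SAP*

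**What the plan says.** Sections 2.2 and 6 define the primary endpoint as the change in phosphorylated eIF2α, XBP1s and BIP/GRP78 in "colon biopsy tissues before and after 6 weeks of TUDCA treatment". The markers are to be measured by Western blot, RT-PCR and immunohistochemistry (IHC).

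Section 6 then describes who does the work. "All the colon biopsy samples will be sent under dry ice for analysis" in the laboratory of the co-PI, who "discovered the therapeutic role of TUDCA in IBD mouse models". A research associate in that laboratory "will be responsible for analyzing and processing data from the clinical samples". The expected direction is stated at the start of the section: "We expect that TUDCA treatment will reduce ER stress in colon biopsy tissues".

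Sections 2.1 and 4.3 make the trial open label, with every patient on TUDCA. Nowhere do the documents mention coded sample labels, masking of laboratory staff or data processing to visit, or running a patient's two samples on one gel, plate or staining batch.

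For the secondary histology endpoint, Section 6.2 (item 3, histologic activity) does specify masking: H&E sections are "evaluated for tissue damage and inflammation by a gastrointestinal pathologist in a double-blinded manner".

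**The concern.** Western blot densitometry involves choices of band boundary, background, exposure and repeat runs, and IHC scoring is a visual grade. If the reader knows which sample is week 6 and expects it to be lower, those choices can lean one way. RT-PCR leaves less room for this. With no control arm, a lean between visits goes straight into the before/after difference and cannot be told apart from a drug effect.

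The plan recognises the issue for a secondary tissue reading but sets no safeguard for the primary one. At stake is whether a significant fall in a small trial can be credited to treatment. Once blots and slides have been read with the visit known, those readings cannot be made masked afterwards.

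**Working it through.** **1. The plan's own figure.** Table 2 in Section 6.1 gives differences of 0.52, 0.48 and 0.30 with SDs of 0.26, 0.24 and 0.15, so the standardised effect is 2.0 for each marker. A two-sided, independent two-sample t-test at 0.05 (non-central t) needs 5.09 per group for 80% power and 6.39 for 90%. Both match Table 2, and 6.39 rounds up to the stated 7 patients. Enrolment is 12. The masking point changes none of these figures.

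**2. Inputs for the bias check.**
- From Section 6.1: significance at P<0.05 (taken as two-sided, which reproduces Table 2), n=7 or n=12, SD half the mean (the text's description), and a sought reduction of 25% to 45%.
- Assumed, because the documents give no value: a systematic under-reading of week-6 values by a fraction s of the mean, and a within-patient correlation ρ.

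**3. Formula.** Suppose there is no true change.
- SD of the paired difference = 0.5 × mean × √(2(1−ρ)). At ρ=0.5 this is 0.5 × mean.
- Standardised shift δ = s / [0.5 × √(2(1−ρ))]. At ρ=0.5, δ = 2s.
- Probability of a significant result in the favourable direction = P(T > t₀.₉₇₅,ₙ₋₁), where T is non-central t with n−1 degrees of freedom and non-centrality δ√n. With δ=0 it is 2.5%.
- Example: s=10%, n=12 gives δ=0.2, non-centrality 0.2 × √12 = 0.693, critical value 2.201, probability 9.2%.

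**4. Results for a single test, SD half the mean, ρ=0.5.**

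| Assumed under-reading | δ | n=7 | n=12 |
|---|---|---|---|
| none | 0 | 2.5% | 2.5% |
| 2% | 0.04 | 3.1% | 3.3% |
| 5% | 0.10 | 4.1% | 5.0% |
| 10% | 0.20 | 6.6% | 9.2% |
| 20% | 0.40 | 14% | 24% |

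For ρ from 0.3 to 0.7, the 10% shift gives 5.7–8.4% (n=7) and 7.7–12.7% (n=12). The 20% shift gives 11–21% and 19–37%.

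**5. Sensitivity to the SD.** The printed Table 2 SDs equal half the differences (0.52/2 = 0.26, 0.48/2 = 0.24, 0.30/2 = 0.15), not half the means as the text says. If they are read as SDs of the paired difference, a shift of 10% of the untreated mean gives these two-sided error rates against a nominal 5%:

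| Marker | δ | n=7 | n=12 |
|---|---|---|---|
| p-eIF2α | 0.116/0.26 = 0.45 | 17% | 29% |
| XBP1s | 0.121/0.24 = 0.50 | 20% | 36% |
| BIP | 0.113/0.15 = 0.75 | 39% | 66% |

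On this reading of the SDs, a 5% shift gives 8–14% (n=7) and 11–22% (n=12).

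**6. Scale.** A 10% shift is 10/45 = 22% to 10/25 = 40% of the reduction the trial is looking for.

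**The case against.** The strongest reply is that silence is not evidence of unmasked reading. The laboratory may code samples as routine. Biopsies are also collected under a separate biobank protocol (Section 5) that is not part of these documents and might cover labelling, though labelling alone would not establish masking to visit. This stands: the documents support only the statement that no masking is specified. A reader might infer that the assays are read unmasked, that the endpoint is biased, or that the co-PI's earlier mouse work casts doubt on the laboratory. The documents support none of these.

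The size also rests on assumed shifts. At 2% or 5% the inflation is small, and one shift applied to all assays overstates the risk for RT-PCR. That stands too, which is why the range is shown and why the rates are for a single test.

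A reader might further infer that splitting a patient's samples across runs adds noise the sample size does not allow for. The documents do not support that. They do not say pairs will be split, the Table 2 sample size is for independent groups and takes no credit for pairing (a paired t-test with the same inputs needs 4.22 and 4.91), and 12 are enrolled against 7 required. Same-run pairing is recommended here so that run differences do not line up with visit.

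Finally, this is a 12-patient Phase I study with a mechanistic aim. That limits the weight of the point, but the plan still tests the primary endpoint at P<0.05.

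**Conclusion.** The point holds as a gap in the plan. Visit masking and same-run pairing are not specified for the primary assays, while a secondary tissue reading is blinded. Followed as written, the plan permits expectation-driven reading of its only primary endpoint, most plausibly in blot densitometry and IHC scoring.

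How much this matters depends on a shift nobody has measured. It is close to negligible at 2%. At 10% the favourable false-positive rate is roughly 2.6 times nominal at n=7 (6.6/2.5) and 3.7 times at n=12 (9.2/2.5), given SD half the mean and correlation 0.5. It is much larger if the printed Table 2 SDs are those of the paired difference.

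Masking would not cure regression to the mean or the absence of a control arm. The case for acting is that the safeguard is cheap and cannot be added after the samples have been read.

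**What to change.** Add to Section 6:
- The site coordinator relabels all biopsies with codes that hide the visit before shipping.
- Both visits of a patient are run on the same gel, plate or staining batch, in random order.
- Laboratory staff and the person processing the data stay masked to visit.
- Quantified values are locked before the code is broken.

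In Section 6.2, state that the histology reader is masked to visit. The present term, double-blinded, does not say to what.

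The cost is coded labels, a run-order list, and frozen storage of baseline samples until the week-6 sample arrives. No additional visit or biopsy is needed, and the sample size does not change.

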6.1 Sample Size Determination for Primary Endpoint

Estimates of change in the primary outcomes: We expect that TUDCA treatment will lead to similar changes on ER stress markers in UC patients as that in IBD mouse models. As judged by quantification results of western blot, the expression levels of ER stress markers in IBD mouse models were significantly reduced by 25% to 45% after TUDCA treatment.⁴ A previous publication, as well as our own data, has shown that standard deviations of the ER stress markers are less than ½ of the means in intestinal biopsy samples of IBD patients⁴⁰. Considering there might be greater variation after the TUDCA treatment, we set the standard deviations at half of the means of all the ER stress markers (Table 2).

Table 2 Sample size calculation

ER stress markers	Difference between means	Estimated standard deviation	Sample size at power=0.8	Sample size at power=0.9
p-elF2α	1.16-0.64=0.52	0.26	5.09	6.39
XBP1s	1.21-0.73=0.48	0.24	5.09	6.39
BIP	1.13-0.84=0.30	0.15	5.09	6.39

Power Estimates for each primary endpoint: We used the quantification results of western blot on ER stress markers to calculate the sample size needed. Since the impact of TUDCA on intestine tissues in humans has not been examined, we used the difference between the mean values of ER stress markers in groups treated with or without TUDCA that we obtained in murine studies.⁴ Power analysis using the R software shows that 7 patients are sufficient to detect the difference before and after the treatment, when P<0.05 is considered significant. Due to the relatively variability in IBD patient disease activity and high dropout rate in IBD clinical trials, we will enroll a total of 12 patients will be recruited for the study with an expected

Statistical analysis: We will be specifically interested in the statistical contrasts that compare before and after TUDCA treatment. Correlation between the primary end point and secondary end point will also be examined. The appropriateness of all analysis of variance and covariance models will be evaluated using regression residuals. If normality or homoscedasticity requirements are violated, data transformations will be explored and, if appropriate transformations cannot be found, analyses may be done semi-parametrically using the ranks of the data.

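### Table 2 takes each SD as half the difference between means, not half the mean as Section 6.1 states, so seven patients being enough does not follow from the stated SD rule

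*Combined protocol and SAP*

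**What the plan says.** The only sample-size justification for the primary endpoint is in Section 6.1 of the combined protocol and SAP.

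- **SD rule.** Human biopsy SDs are reported to lie below half of the mean. To allow for more spread once patients are on the drug, the section states: "we set the standard deviations at half of the means of all the ER stress markers". It points to Table 2 for the values.
- **Effect.** It comes from mice: "we used the difference between the mean values of ER stress markers in groups treated with or without TUDCA". Table 2 prints "1.16-0.64=0.52" for p-eIF2α, 1.21 and 0.73 (difference 0.48) for XBP1s, and "1.13-0.84=0.30" for BIP. The SDs beside them are 0.26, 0.24 and 0.15. All three rows give 5.09 for 80% power and 6.39 for 90%.
- **Conclusion.** "Power analysis using the R software shows that 7 patients are sufficient to detect the difference before and after the treatment", at a significance level of 0.05. Variability and the "high dropout rate in IBD clinical trials, we will enroll a total of 12 patients" are the reasons for going beyond seven.
- **Analysis.** "We will be specifically interested in the statistical contrasts that compare before and after TUDCA treatment". Section 4.3 confirms that there is a single treated group.

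The section names R but not the test or its sidedness. It gives neither an SD of within-patient change nor a before/after correlation.

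**The concern.** Three markers with different means and differences should not all need the same number of patients. They do so in Table 2 because each SD was obtained by halving the difference, which fixes difference/SD at 2 whatever the marker. The text describes a cautious rule tied to human biopsy data; the table applies a much smaller SD that has no stated basis.

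The printed sizes also look like numbers per group for two independent groups, whereas this trial has one group measured twice. The precision of such a comparison depends on the within-patient correlation, which is not given.

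At stake is how the 12 enrolled patients are understood. If seven were enough, five could be lost without harm. If seven are not enough, there may be little or no reserve. A null result for BIP, one of the three markers named in the primary endpoint, could then be read as absence of effect when the study had little chance of showing one.

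**Working it through.** **Inputs (Section 6.1, Table 2).** Untreated and treated means: p-eIF2α 1.16 and 0.64; XBP1s 1.21 and 0.73; BIP 1.13 and 0.84. Differences: 0.52, 0.48, 0.30. The printed BIP means give 0.29; unrounded means could give 0.30, so both are carried. Alpha is 0.05, taken as two-sided.

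**Formulas.** Power is the probability that a noncentral t variable exceeds the two-sided 5% critical value in absolute size.
- Two groups: df = 2(n−1), noncentrality = (difference/SD)·√(n/2), n per group.
- Paired: df = n−1, noncentrality = (difference/SD of change)·√n.

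**1. Reproducing Table 2.** With difference/SD = 2, the two-group test needs 5.09 (80%) and 6.39 (90%) per group, as printed. A one-sided two-group test gives 3.99 and 5.13. A paired test with the table's SD as the SD of change gives 4.22 and 4.91. Of the variants tried, only the two-sided two-group test matches.

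**2. Table SDs against the stated rule.**

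| Marker | Table SD | Half the difference | Half the untreated / treated mean | Table SD as share of untreated / treated mean |
|---|---|---|---|---|
| p-eIF2α | 0.26 | 0.26 | 0.58 / 0.32 | 22% / 41% |
| XBP1s | 0.24 | 0.24 | 0.605 / 0.365 | 20% / 33% |
| BIP | 0.15 | 0.15 | 0.565 / 0.42 | 13% / 18% |

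No choice of mean produces the table's values.

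**3. Stated rule in the table's own test.** This checks the plan's consistency; it does not measure the trial's power. With the SD at half the untreated, average or treated mean, power at 7 per group is:
- p-eIF2α: 34%, 51%, 79.7%
- XBP1s: 28%, 40%, 62%
- BIP: 14–15%, 17–18%, 22–23%

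The number per group for 80% power runs from 7.05 to 20.5, 10.1 to 25.9 and 31.8 to 60.6, against the printed 5.09.

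**4. Stated rule in a paired test.** Each time point's SD is half its own mean, and r is an assumed correlation:

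SD of change = √(s₁² + s₂² − 2·r·s₁·s₂)

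For p-eIF2α at r = 0.5: √(0.3364 + 0.1024 − 0.1856) = 0.503. XBP1s and BIP give 0.528 and 0.508.

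| r | Pairs for 80% power: p-eIF2α / XBP1s / BIP | Power at 7 | Power at 12 |
|---|---|---|---|
| 0 | 15 / 20 / 46–49 | 42% / 33% / 15–16% | 70% / 57% / 26–27% |
| 0.3 | 12 / 15 / 33–35 | 52% / 42% / 19–20% | 82% / 71% / 34–36% |
| 0.5 | 10 / 12 / 25–27 | 63% / 52% / 25–26% | 90% / 82% / 44–46% |
| 0.7 | 8 / 9 / 17–18 | 77% / 68% / 36–38% | 97% / 93% / 62–65% |
| 0.8 | 7 / 8 / 13 | 86% / 79% / 47–50% | 99% / 98% / 77–79% |

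The correlation needed for 80% power is about 0.73, 0.81 and 0.93 with 7 pairs, and about 0.26, 0.47 and 0.80–0.82 with 12.

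**5. Which mean is halved.** The most favourable reading uses one SD, half the treated mean, at both time points. At r = 0.5 the SD of change equals that SD, and 7 pairs give 94%, 82% and 34–36%. Across all readings and r up to 0.7, BIP at 7 pairs stays between 13% and 53%. With 12 pairs BIP reaches 80% at a correlation of about 0.7 (half the treated mean), just under 0.8 (half the average mean), 0.80–0.82 (own means) or about 0.83 (half the untreated mean).

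**The case against.** The best defence is that only the SD matters and that the table may be what was meant.

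- **The formula alone is harmless.** With Table 2's SDs, a paired test at 80% power needs 5 patients if they are SDs of change, or 7 (from 6.11) if they are per-time-point SDs with zero correlation. This stands: the two-group formula mismatches the design but would not by itself overturn seven at 80% power. That this formula was used is also inferred from the exact match, since the plan does not name the test.
- **The text may be the slip.** If half of the difference was intended, the table stands and seven follows. But the text ties its rule to human biopsy SDs relative to their means and to extra variation after treatment. Half the difference has no link to either.
- **Half the mean is a ceiling.** The human SDs are reported as below that, so the table's SDs do not contradict the human data, and the recomputed powers are cautious ones. This stands, but it is the ceiling that the plan says it used.
- **The correlation is assumed.** This stands too. At 0.8 two markers need only 7 or 8 pairs. The claim is that seven is unsupported, not that it is shown to be too few for every marker.
- **BIP's 0.29 or 0.30** is compatible with rounding and changes nothing material.

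**Conclusion.** The concern holds. That text and table disagree on the SD needs no assumption, and the statement that seven patients are enough rests on the table's smaller SD. Under the written rule, no marker reaches 80% power at seven in the table's own test, although p-eIF2α at 79.7% comes within rounding under the most favourable choice of mean. In a paired test the answer turns on which mean is halved and on an unstated correlation.

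With SDs at half of each time point's own mean and an assumed correlation of 0.5, the implied reserve of 12 − 7 = 5 patients becomes 12 − 10 = 2 for p-eIF2α, 12 − 12 = 0 for XBP1s, and a shortfall of 13 to 15 for BIP. Twelve completers could be adequate for the first two markers. BIP is likely underpowered at 12 unless the correlation is about 0.8, or about 0.7 if the SD is half the treated mean. The actual power cannot be fixed from the documents. The statement needs correcting because it is the only sample-size support for the primary endpoint.

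**What to change.** In Section 6.1:

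1. Make text and Table 2 use the same SD. If the rule stays at half of the means, say which mean; if another SD is meant, give its source.
2. Recompute Table 2 with a two-sided paired t-test, naming the test. Use a sourced SD of within-patient change or, failing that, the stated SDs over a range of correlations such as 0 to 0.8.
3. Check whether the BIP difference is 0.29 or 0.30.
4. Delete or qualify the statement that seven patients suffice. Give power per marker at 7 and at 12 evaluable patients.
5. Keep enrolment at 12.

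Possible wording, if each time point's SD is half its own mean: *With a two-sided paired t-test at the 5% level and an assumed within-patient correlation of 0.5, 12 evaluable patients give about 90% power for p-eIF2α, 82% for XBP1s and 44–46% for BIP; 7 give about 63%, 52% and 25–26%. On these SDs, BIP reaches 80% power with 12 patients only if the correlation is about 0.8 or more.*

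The cost is a recalculation and rewording of one section, with no extra patients or procedures. The stated power becomes less favourable, most clearly for BIP.
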